8.4.3.2. Follow-up Visits / Remote CareLink Transmissions

Subjects are required to perform a manual CareLink transmission at 3, and 9 months following successful Reveal LINQ ICM insertion.

CareLink transmission data will be automatically transferred to the Medtronic Data Warehouse for CareLink. If unavailable, sites may be asked to submit CareLink reports by uploading them to a secure server or sending printed versions of the CareLink reports to Medtronic. Printouts only need to be provided to Medtronic upon request.

8.4.4. Unscheduled Follow-up Visits

An unscheduled visit is defined as any unplanned cardiology or neurology visit by the subject to the study site. Routine visits or other planned visits are not collected.

The following information is required to be collected at unscheduled follow-up visits:

- Reveal LINQ Interrogation (if available, subjects with a Reveal LINQ ICM only)
- AF Assessment
- Symptom Assessment
- Stroke/TIA Assessment
- Adverse Event e-CRF (if applicable)

8.4.5. Stroke/TIA Recurrence

Following the index event, a subject should be monitored for stroke recurrence. If there is a stroke/TIA recurrence, the following data is required to be collected:

- Details about the stroke event, such as type, size, and location.
- TOAST stroke classification
- National Institute of Health (NIH) Stroke Scale
- Modified Rankin Scale
- Reveal LINQ Interrogation (if available, subjects with a Reveal LINQ ICM only)
- AF Assessment
- Adverse Event e-CRF

8.4.6. System Modification

A system modification will be reported in the event the Reveal LINQ ICM requires invasive modification (e.g., explant, replacement, repositioning).

• If the modification consists of repositioning or replacement, the follow-up schedule for the subject will remain unchanged.

18 December 2018 Version 4.0 Page 34 of 66

If the Reveal LINQ ICM is explanted, the subject should continue participation in this study and a
crossover e-CRF is required. If the subject receives implant of another Medtronic device (IPG,
ICD or CRT) reference Table 8 for recommended programming parameters for these devices.
The other parameters for these devices are to be programmed based on the investigator's
opinion.

Table 5: Recommended Programming Parameters for Medtronic IPG, ICD or CRT Devices

Parameter	Recommended Setting
Atrial preference pacing (APP)	OFF
Atrial rate stabilization (ARS)	OFF
Post-mode switch overdrive pacing (PMOP)	OFF
Atrial Anti-tachycardia pacing (ATP)	OFF
AT/AF detection and EGM collection	Nominal

The following will be collected in the event of a system modification:

- Reason for modification
- System/Procedure Information
- Pre-modification: device interrogation
- Post-modification: device interrogation (if modification includes a Medtronic device)

All explanted product should be returned to Medtronic for analysis when permissible by local laws and regulations.

8.4.7. Study Exit

A study exit e-CRF is required for all subjects except in the case of death. Prior to exiting a subject from the study, it is recommended to follow the subject until all ongoing system and/or procedure related AEs are resolved or unresolved with no further actions planned. Following exit, subjects should continue to receive standard medical care. Upon exiting from the study, no further study data will be collected or study visits will occur for the subject. All data available through the time of the subject's exit will be used for analysis.

Subjects are urged to remain in the study as long as possible but may be exited from the study for any of the following situations:

- Subject lost to follow-up
- Subject did not meet inclusion/exclusion criteria and not randomized
- Subject not randomized
- Subject did not provide consent or data use protection authorization

18 December 2018 Version 4.0 Page 35 of 66

- Subject chooses to withdraw (e.g., consent withdrawal, relocation to another geographic location)
- Investigator deems withdrawal necessary (e.g., medically justified, inclusion/exclusion criteria not met, failure of subject to maintain adequate study compliance)
- Subject with a Reveal LINQ ICM that has reached end of device life (continuous monitoring patients only)
- Subject has completed 3 years of follow-up
- Study Closure

The following information is required to be collected at study exit on the study exit e-CRF:

- Date of exit
- Reason for exit
- Reveal LINQ Interrogation (if available, subjects with a Reveal LINQ ICM inserted only)
- AF Assessment (except in the case of lost to follow-up or death)
- Stroke/TIA Assessment (except in the case of lost to follow-up or death)

In the case that the subject is determined to be lost to follow-up, details of a minimum of two attempts and the method of attempt (e.g., one letter and one phone record or two letters) to contact the subject must be documented. In addition, follow the regulations set forth by the governing Ethics Committee.

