5.1. Study Design

Stroke AF is a prospective, multi-site, randomized, controlled, non-blinded, post-market study. The Stroke AF study will compare the incidence rate of AF through 12 months between the continuous monitoring arm and the control arm in subjects with a recent ischemic stroke of presumed known origin. Once enrolled, subjects will be randomized 1:1 (continuous monitoring vs control). Subjects randomized to the continuous monitoring arm will have a Reveal LINQ ICM inserted within 10 days of the qualifying stroke and undergo continuous remote monitoring. Subjects randomized to the control arm will be followed per site specific standard of care.

The study is expected to be conducted at approximately 40 sites located in the United States (U.S.).

It is estimated that approximately 496 subjects will be enrolled in the study. Assuming 2% attrition from enrollment to randomization, approximately 486 subjects will have randomized. A total of 23 first documented AF events within 12 months of randomization are required for the study to test the primary objective. AF will be defined as an AF event lasting more than 30 seconds and adjudicated by the endpoint adjudication committee. The analysis of the primary objective will occur after all enrolled subjects have completed 12 months of follow-up. Approximately 248 devices may be used in the study. Based on previous studies of this scope and magnitude, it is estimated that sites may identify and enroll on average one eligible subject per month.

To ensure a widespread distribution of data and minimize site bias in study results, the maximum number of subjects who may be enrolled at a single site is 50 subjects. Sites that enroll faster than others will be allowed to do so in order to maintain an adequate overall study enrollment rate. In addition, to ensure a robust dataset is available for subgroup analysis, a maximum of 50% (approximately248) subjects with lacunar stroke (i.e., small vessel disease) may be enrolled. Medtronic will notify study sites when enrollment of lacunar stroke subjects is no longer allowed, if applicable.

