8.3. Randomization and Treatment Assignment

Subjects are eligible for randomization assignment after study enrollment and verification of eligibility criteria. Enrollment, randomization and insertion of the Reveal LINQ ICM must occur within 10 days of the qualifying stroke event.

Subjects will be randomized in a 1:1 fashion to the continuous monitoring arm (Reveal LINQ ICM) or control arm (standard of care) using the RDC electronic system. Randomization schedules will be created by a statistician and randomization assignments will be automatically populated on the Randomization e-CRF after subject consent and eligibility verification have been entered in RDC. The randomization schedule will be stratified by study site to ensure 1:1 randomization within each study site.

Once subjects are assigned to a study arm (continuous monitoring or control), they are considered randomized. All randomized subjects should be encouraged to comply with the Stroke AF study procedures until study closure and every effort should be made to avoid crossover. Statistical analysis will be done on an intention to treat basis unless otherwise specified. Therefore, once a subject is assigned to an arm, he/she will remain in this arm and all efforts will be made to provide the optimal therapy specified per the assigned treatment arm. In case this is clinically or technically not feasible, the intention to treat is assured. A per-protocol analysis cohort will also be defined within the statistical analysis plan (SAP) and additional supportive analyses of the objectives may be performed in this cohort.

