8.8. Subject Withdrawal or Discontinuation

Subjects will be followed until study closure.

9. Risks and Benefits

Medtronic follows rigorous Quality Assurance and Control procedures throughout the life of a product, from the business analysis phase through development, market release, and post-market surveillance.

The Stroke AF study system and components are commercially released and used in accordance with their approved labeling. The safety and clinical performance of these devices has been demonstrated through previous pre-clinical testing and previous clinical studies. There are no incremental risks introduced to the subject as a result of participation in the Stroke AF study. Devices should be handled in accordance to the Clinical Manual.

For subjects with a Reveal LINQ ICM inserted, Risks and Risk Mitigations to the subject identified below are consistent with those outlined in the device manual. There may be other discomforts and risks related to the device system and/or this study that are not foreseen at this time.

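### Protocol 8.4.7 lets an investigator end follow-up of a randomized subject for unmet eligibility criteria, which could cause arm-dependent informative censoring

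*Protocol*

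**What the plan says.** Protocol 8.4.7 lists the grounds for exit. One line covers the subject found ineligible before assignment: "Subject did not meet inclusion/exclusion criteria and not randomized". A second covers anyone else who was not randomized. A further line gives the investigator discretion: "Investigator deems withdrawal necessary (e.g., medically justified, inclusion/exclusion criteria not met, failure of subject to maintain adequate study compliance". This line does not mention randomization status.

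The effect of exit is complete: "Upon exiting from the study, no further study data will be collected or study visits will occur for the subject". Data collected earlier are kept: "All data available through the time of the subject's exit will be used for analysis". The exit form calls for an AF assessment, except after loss to follow-up or death, and for a device interrogation if one is available.

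Other sections point the other way:

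- Protocol 8.8, on withdrawal, consists of one sentence: "Subjects will be followed until study closure".
- Protocol 8.3 commits to intention to treat and says "All randomized subjects should be encouraged to comply with the Stroke AF study procedures until study closure".
- Protocol 8.4.2 keeps a subject who leaves the insertion procedure without an ICM on the same visit schedule. Protocol 8.4.6 keeps a subject whose ICM is explanted in the study.

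On timing and blinding, 8.3 says "Subjects are eligible for randomization assignment after study enrollment and verification of eligibility criteria", and 5.1 says "Stroke AF is a prospective, multi-site, randomized, controlled, non-blinded, post-market study".

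**The concern.** Non-randomized subjects are already covered, so the practical effect of the eligibility ground in the investigator line is to reach randomized subjects. Their endpoint follow-up can then be cut short at the discretion of someone who knows the arm.

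The eligibility criterion makes this more than a formality. Inclusion (7.3) depends on what the stroke is believed to be due to, and 7.4 excludes cryptogenic and cardioembolic strokes. Protocol 3.1 itself says that the cause is often hard to establish and that many patients have several candidate causes. Enrollment, randomization and insertion must all fit within 10 days of the stroke, so some of the work-up may arrive later. A new suspicion of a cardioembolic source is closely tied to a suspicion of AF, which is the endpoint.

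A subject exited at that moment, with AF suspected but not yet documented, is censored at last contact or last usable device data (Protocol 12.1 vi, SAP 7.9). The log-rank test treats that censoring as unrelated to AF risk. It may also differ by arm: the ICM records continuously, while a control subject is monitored according to site standard of care.

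The SAP has little to catch this. Section 6.1 assumes the same 10% attrition in each group. Section 7.4 regards only subjects with no follow-up time as missing. Section 7.1.1 summarizes exits by reason without saying that this will be done by arm.

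**Working it through.** **1. The text.** The exit list has two lines for non-randomized subjects and one investigator line with no such limit. Setting 8.4.7 beside the other sections:

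| Situation after randomization | Follow-up for AF | Source |
|---|---|---|
| No ICM in place after the procedure | continues unchanged | 8.4.2 |
| ICM explanted | continues | 8.4.6 |
| Found not to meet criteria | may end completely | 8.4.7 |
| Any subject | to study closure | 8.8 |

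The third row is out of line with the others. Section 8.8 read literally would also conflict with other exit grounds, such as lost to follow-up, so it shows that the sections need reconciling more than it shows a deliberate ban.

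**2. The plan's own figures.** Inputs from SAP 6.1: 486 randomized 1:1 (243 per arm), event-free rates 92% and 98%, 10% annual attrition, 5% annual crossover in each arm, one year, two-sided alpha 0.05.

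- Hazard ratio = ln(0.92)/ln(0.98) = 4.13, as stated.
- Expected events in a Lakatos-type model with attrition and crossover: 18.1 ICM + 5.0 control = 23.1, which agrees with the stated 23.
- Simulated log-rank power with these inputs: 83.2% (20,000 runs), close to the stated 85%. The analytic Lakatos calculation gives 80.3%. Each is used below only as a baseline for changes.

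**3. Exits unrelated to AF** (analytic baseline 80.3%; extra exits at day 0; exit rates assumed):

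| Extra exits | ICM arm only | Control arm only |
|---|---|---|
| 5% | 79.9% | 78.7% |
| 10% | 79.4% | 77.0% |

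The effect is small.

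**4. Exits that remove would-be AF events in one arm** (simulation, baseline 83.2%; 8,000 runs each; fractions assumed):

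| Lost would-be events | Events lost | Rejection rate |
|---|---|---|
| 10% of ICM arm | about 1.8 | 74.1% |
| 20% of ICM arm | about 3.6 | 62.9% |
| 20% of control arm | about 1 | 90.1% |
| 40% of control arm | about 2 | 95.3% |

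**5. The same in crude hazard ratios**, without attrition or crossover. Planned events are 243 × 0.02 = 4.86 control and 243 × 0.08 = 19.44 ICM.

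- One control event lost: 3.86/243 = 1.59%; ln(0.92)/ln(1 − 0.0159) = 5.2.
- One ICM event lost: 18.44/243 = 7.59%; ln(1 − 0.0759)/ln(0.98) = 3.9.

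**6. How likely is the loss of one control event?** The documents give no rate of late-found ineligibility. If it were 2% to 5%, then 10 to 24 of 486 subjects would be affected, about 5 to 12 of them controls. At the planned 2% AF rate these controls carry 5 × 0.02 = 0.1 to 12 × 0.02 = 0.24 expected events. Losing a whole event requires an AF risk among them of about 1/12 = 8% to 1/5 = 20%, that is, 4 to 10 times the planned rate. Parts 4 and 5 therefore show sensitivity; they are not forecasts.

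**The case against.** The strongest reply is that the chain to bias is narrow. Eligibility is verified before assignment, and Table 2 schedules that assessment at baseline only. AF found later is not prior history and need not overturn what was believed at baseline. No section asks investigators to reassess eligibility. A rhythm finding strong enough to reclassify the stroke may itself be the adjudicable event, and it counts if dated before exit. An AF assessment is required at exit, and 8.4.3.1 calls for source documents from any test that detects AF. SAP 7.1.1 also tabulates follow-up time and visit attendance by arm, so a gross imbalance would show. All of this stands and limits the likely harm.

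The reply also notes that the exit lines overlap, so the investigator line was perhaps not meant for randomized subjects. That is possible, but as written the line reaches them.

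Several stronger readings are tempting, and the documents do not support them:

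- A reader might infer that 8.4.7 breaks a rule in 8.3. Section 8.3 encourages compliance and sets the analysis principle; it forbids no exit. The relation is one of tension.
- A reader might infer that exited subjects leave the primary analysis. Protocol 12.1 vii includes all randomized subjects, and data up to exit are used. The point is lost follow-up. How SAP 7.1.3 words its cohorts is a separate matter that is not relied on here.
- A reader might take the hazard ratio of 5.2 as the expected bias, or as bias in the device's favor. It is a chosen scenario, and losses in the ICM arm act in the opposite direction.
- A reader might extend the argument to exit for poor compliance. That ground also truncates follow-up, but the case made here concerns the link between doubt about eligibility and suspected AF, which does not carry over.

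**Conclusion.** The point holds as a weakness in the wording of the plan. In a non-blinded trial whose eligibility depends on a revisable judgment of stroke cause, 8.4.7 permits discretionary truncation of AF follow-up after randomization. It conflicts with 8.8 and is inconsistent with the retention rules in 8.4.2 and 8.4.6.

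The documents show neither that such exits occur nor how often, nor which arm they would affect. Bias requires exits related to both arm and AF risk. The size is conditional on that: losing one or two would-be control events, or about two to four ICM events, moves the rejection rate anywhere from about 63% to 95% around a baseline of 83%. The sensitivity arises because only about 5 control events are expected. The change is worth making as an inexpensive improvement; it is not a defect that undermines the primary analysis.

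**What to change.** - In Protocol 8.4.7, confine exit for unmet inclusion or exclusion criteria to subjects who have not been randomized.
- State that a randomized subject later found ineligible is recorded as a study deviation and stays on the unchanged visit and AF-assessment schedule. Section 8.7 already requires deviations to be reported; what is new is the instruction to continue follow-up.
- Reconcile 8.4.7 with 8.8, so that the two sections agree on when follow-up may end.
- In SAP 7.1.1, tabulate exit reasons by randomized arm.

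Consent withdrawal, medically justified exit and the compliance ground are left as they are. Some discretion therefore remains under the medical ground, and the table by arm helps to make its use visible.

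The cost is an amendment to the wording, one extra table, and continued follow-up of a few subjects who are already enrolled and budgeted.

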5.2. Duration

The enrollment period is expected to start in early 2016 and will take approximately 42 months. Subjects will be followed for 3 years, until end of device life or until official study closure, whichever occurs first. Therefore, the expected study duration from first enrollment to official study closure (final report) is approximately 6.5 years. The duration of individual subject participation will vary based on timing of site activation and their enrollment; however, at a minimum, participation of an individual subject will be for 3 years, until end of device life or until study closure, whichever occurs first.

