8.4.2. Reveal LINQ ICM Insertion

The insertion procedure must occur within 10 days of the qualifying stroke event and after randomization. The insertion will be performed in accordance with the hospital's standard insertion practice and in accordance with the Medtronic Reveal LINQ ICM insertion instructions which are found within the Reveal LINQ ICM Clinician manual. The following information is required to be collected at the insertion visit:

- System and Procedure Information
 - System and procedure details will be collected including, but not limited to procedure date, device serial number, location of insertion procedure, location/orientation of inserted device, antibiotic use, and closure method.
- Device Programming/Interrogation
 - Programming requirements for the Reveal LINQ ICM are outlined in Table 6 below. A full device interrogation will be collected after final programming. Programming changes will be allowed only when clinically necessary. All deviations from the programming guidelines (regardless of when they occur) must be documented on a Study Deviation e-CRF, including the rationale for the deviation.

18 December 2018 Version 4.0 Page 31 of 66

Table 3: Reveal LINQ ICM Programming

Parameter	Required Setting
Reason for Monitoring	Cryptogenic Stroke
AF Detection Sensitivity	Balanced Sensitivity
Ectopy Rejection	Aggressive
AT/AF Recording Threshold	All Episodes
Type of AT/AF Detection	AF Only
Wireless Data Priority	Tachy, Pause, Brady
Tachy Detection	ON
Brady Detection	ON
Pause Detection	ON

The subject will be instructed about the use of the Medtronic MyCareLink Monitor and the Patient Assistant.

If the subject does not have a Reveal LINQ ICM device in the body at the conclusion of the procedure, the subject should remain in the study and the follow-up schedule remains unchanged. For these patients, CareLink transmissions at 3 and 9 months are not required.

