### Recurrent Stroke Subgroups

Subgroup analysis for subjects with recurrent stroke and without recurrent stroke will be presented. Stroke events adjudicated by the CEC will be used to identify subgroups.

- If a subject has at least one stroke event as adjudicated by the CEC during the follow-up period, then the subject is in the "Stroke" subgroup
- If a subject does not have any stroke events as adjudicated by the CEC during the follow-up period, then the subject is in the "No Stroke" subgroup

The number of events and the number of subjects in each subgroup will be reported overall and within each randomization arm. A logistic regression model will be used to test the interaction between treatment and subgroup.

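### Exit at device end of life is open to the monitoring arm only, and the by-arm stroke and adverse event counts do not allow for any shorter follow-up that results

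*Protocol*

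**What the plan says.** **Planned length of follow-up.** Protocol 5.2 states: "Subjects will be followed for 3 years, until end of device life or until official study closure, whichever occurs first". The synopsis, Protocol 12.1.v and SAP 3 and 6.1 repeat this limit for subjects in general. Protocol 8.8 states something different: "Subjects will be followed until study closure".

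**Exit rule.** Protocol 8.4.7 introduces its list of exit reasons with "Subjects are urged to remain in the study as long as possible but may be exited from the study", and one item is "Subject with a Reveal LINQ ICM that has reached end of device life (continuous monitoring patients only". The same section adds: "Upon exiting from the study, no further study data will be collected".

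**Other subjects without a working device.** After an insertion procedure that leaves no device in the body, Protocol 8.4.2 says "the subject should remain in the study and the follow-up schedule remains unchanged". Protocol 8.4.6 says: "If the Reveal LINQ ICM is explanted, the subject should continue participation in this study".

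**Analysis of stroke and adverse events.** SAP 7.8 classes subjects by whether they had any adjudicated stroke during follow-up. It then says: "The number of events and the number of subjects in each subgroup will be reported overall and within each randomization arm". A logistic regression follows, with no term for follow-up time. SAP 7.10 summarises adverse events as counts and percentages. SAP 7.1.1 tabulates follow-up time by randomization group.

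**Analysis of AF.** Both AF objectives use Kaplan-Meier curves and a log-rank test. Subjects without AF are censored at the later of last contact or last usable device data, capped at 12 months for the primary objective.

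**The concern.** A control subject has no device that can expire, so this exit can shorten follow-up in one randomized arm only. Any stroke, death or cardiovascular event after such an exit goes unrecorded in the monitoring arm, whereas the same event in a control subject is recorded up to 36 months. A raw count, a percentage of subjects with an event, or a logistic model for ever having had an event treats both arms as if they had been observed for the same time. It would therefore favour the monitoring arm when the true rates are equal.

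This matters most for recurrent stroke. The protocol's background and purpose present AF detection as a way to reduce recurrent stroke, so readers will look at the stroke numbers by arm even though stroke is neither a primary nor a secondary objective.

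**Working it through.** The plan gives no figure for follow-up by arm or for device life, so there is nothing of its own to reproduce. The check sizes the possible imbalance.

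**Inputs from the documents**
- Attrition of 10% per year in each group (SAP 6.1 and 6.2): λ = −ln(0.90) = 0.1054 per year.
- 486 randomized 1:1, or 243 per arm.
- Maximum follow-up of 3 years in both arms.
- Device monitoring for up to 3 years (Protocol 3.1). No minimum, mean or distribution is given.

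**Assumptions**
- Every monitoring-arm device ends at the same time L, and every such subject is exited then. This is a worst case for each L.
- True event rates are constant and equal in the two arms.

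**Person-years per subject** = (1 − e^(−λL)) / λ = (1 − 0.9^L) / 0.1054

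| L (monitoring arm) | Person-years per subject | Ratio to control (L = 3) |
|---|---|---|
| 2.5 y (30 months) | 2.20 | 0.85 |
| 2.75 y (33 months) | 2.39 | 0.93 |
| 3.0 y (36 months) | 2.57 | 1.00 |

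For 243 subjects, control contributes about 625 person-years. The monitoring arm contributes about 534, 580 or 625. With equal constant rates, the expected total event count falls in the same ratio.

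**If only a share s exits at 30 months**, the ratio is 1 − s(1 − 0.854). For s = 0.25 it is 0.96, and for s = 0.50 it is 0.93.

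**Subjects with a first stroke.** Let p be an assumed annual first-stroke risk and μ = −ln(1 − p). The expected number per arm is 243 × μ/(μ + λ) × (1 − e^(−(μ + λ)L)).

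| Assumed p | Control, 36 months | Monitoring arm, all exit at 30 months | Ratio |
|---|---|---|---|
| 3% | 18.2 | 15.7 | 0.86 |
| 5% | 29.8 | 25.8 | 0.86 |
| 10% | 56.9 | 49.8 | 0.87 |

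The ratio hardly depends on the assumed stroke rate. It depends on when devices end and on how many subjects are then exited.

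**After adjustment.** Under the same assumptions, events per person-year or a hazard ratio have a monitoring-to-control ratio of 1.00 at any L.

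**The case against.** Three stronger readings are tempting, and the documents support none of them.

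- **Follow-up is shorter in the monitoring arm by design.** The exit is permissive, subjects are urged to stay, both arms stop at 3 years, and the only device-life figure equals that cap. Follow-up differs only if devices end early and the subjects are then exited. Neither is established, and the shortfall may be zero. The permissive wording is not a full answer, though. It also governs completion of 3 years and study closure, and Protocol 5.2 names device end of life as a planned end of follow-up.
- **Total adverse events will look lower in the monitoring arm.** Protocol 10.1.1 collects device- and procedure-related events, which arise essentially only in subjects with an ICM and raise that arm's count. SAP 7.10 does not specify a comparison by arm either. The tilt can be argued only for events that both arms can have.
- **The secondary AF comparison is biased.** It censors at last contact or last usable device data. Battery end of life is close to administrative censoring, and unequal censoring between arms does not in itself bias a log-rank test. What remains is that AF found clinically after such an exit is not recorded.

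Two further defences have weight. AF and stroke assessments are required at exit, so events up to that point are captured. The SAP 7.1.1 table of follow-up time by arm would show an imbalance, but it would not correct the stroke or adverse event results.

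The explant and failed-insertion rules are not in strict contradiction with the exit rule, because a rule that subjects should stay and a rule that others may leave can both be followed. They do treat loss of a working device differently according to its cause, without giving a reason. The plainer conflict is between Protocol 8.8 and Protocol 5.2 and 8.4.7.

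**Conclusion.** The point holds in a limited form. One arm alone has an exit at device end of life, data stop at exit, and the planned stroke and adverse event summaries carry no exposure adjustment. Shared events may therefore look fewer in the monitoring arm with no true difference.

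The size is unknown. Under full exit and 10% annual attrition it runs from no effect at 36 months to about 7% fewer events at 33 months and 15% fewer at 30 months. It is smaller if only some subjects exit. These figures rest on an assumed common device life and on constant, equal event rates.

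The 12-month primary objective is untouched unless a device ends within the first year. The secondary log-rank test is largely protected by censoring. The affected results are supportive ones, and the correction costs little.

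**What to change.** 1. **SAP 7.8, recurrent stroke.** Replace the raw comparison by arm and the logistic model with time to first adjudicated stroke from randomization (Kaplan-Meier by arm and a Cox hazard ratio), censored at exit, death or last contact. Events per person-year are an acceptable alternative. If the event rate changes with time since the index stroke, time-to-event is the better choice, because crude rates over unequal follow-up would not compare like with like.
2. **SAP 7.10, safety.** For any comparison by arm of deaths and cardiovascular events, use the same methods or rates per person-year. Report device- and procedure-related events separately, because control subjects are essentially not exposed to them.
3. **Protocol 5.2, 8.4.7 and 8.8.** Reconcile these on when follow-up ends and whether device end of life ends it. State how this fits with the retention of explanted and failed-insertion subjects in 8.4.6 and 8.4.2.

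Removing the device-life exit altogether is more debatable. It would give both arms the same planned follow-up, but it would add unmonitored time to the monitoring arm in the intention-to-treat secondary analysis. Items 1 and 2 remove the problem without it.

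The cost is slightly more analysis work and a short wording change. The exit date and last-contact date needed for the denominators are already planned for the SAP 7.1.1 follow-up table.
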